#### 2 TRIAL OBJECTIVES AND ENDPOINTS

#### 2.1 **Objectives**

#### Primary Objective

• To compare a starting dose of 15 µg REKOVELLE to a starting dose of 225 IU GONAL-F in conventional regimens with respect to ovarian response in women undergoing controlled ovarian stimulation

#### **Secondary Objectives**

- To compare the follicular development, endocrine profile and embryo development associated with conventional dosing of REKOVELLE and GONAL-F
- To compare the treatment efficiency associated with conventional dosing of REKOVELLE and GONAL-F
- To compare the safety profile associated with conventional dosing of REKOVELLE and GONAL-F

#### 2.2 Endpoints

#### **Primary Endpoint**

• Number of oocytes retrieved

#### **Secondary Endpoints**

- Number of follicles (total and by size category) at end-of-stimulation
- Serum concentrations of estradiol and progesterone at end-of-stimulation
- Number of fertilised oocytes and fertilisation rate
- Number of blastocysts (total and by quality)
- Total gonadotropin dose and number of stimulation days
- Early OHSS (overall and by grade) and/or preventive interventions for early OHSS

#### **Exploratory Assessment**

• Blood sample on stimulation day 1 for potential future analysis of possible biomarkers associated with ovarian response (requires additional, optional consent)

#### Follow-up Assessments

• Clinical pregnancy rate (at least one gestational sac 5-6 weeks after transfer) in the first transfer cycle

• Implantation rate (number of gestational sacs 5-6 weeks after transfer divided by number of blastocysts transferred) in the first transfer cycle

*Note:* the first transfer cycle covers cycles with transfer occurring within 3 months after start of stimulation

#### 3 TRIAL DESIGN

#### 3.1 Overall Design and Control Methods

#### Trial period

This is a randomised, controlled, assessor-blind, parallel groups, multicentre, multinational trial comparing the ovarian response associated with a starting dose of 15  $\mu$ g follitropin delta (REKOVELLE) and a starting dose of 225 IU follitropin alfa (GONAL-F) in conventional regimens. The primary endpoint is the number of oocytes retrieved, and secondary endpoints include pharmacodynamic parameters of FSH action as well as efficacy and safety parameters related to controlled ovarian stimulation. Treatment efficiency in terms of gonadotropin use and duration of stimulation will also be evaluated. The assessor-blind design ensures that the investigators and other assessors such as embryologists are blinded to individual treatment allocation. A trial medication delegate will be responsible for all trial medication related issues, both practically at the clinic and in interactions with the subject.

Subjects will be screened within 90 days prior to randomisation for compliance with the inclusion and exclusion criteria. On day 2-3 of the menstrual cycle, subjects will be randomised in a 2:1 ratio to treatment with either REKOVELLE or GONAL-F, and stimulation will be initiated. Subjects randomised to REKOVELLE will receive a daily starting dose of 15  $\mu$ g which will be fixed for at least the first four stimulation days. Dose adjustments may be implemented on the day of starting the GnRH antagonist (stimulation day 5 or day 6) or later, and can occur no more frequently than once every second day. At each dose adjustment, the daily REKOVELLE dose can be increased or decreased by 5  $\mu$ g based on the subject's response. The minimum REKOVELLE dose is 5  $\mu$ g and the maximum REKOVELLE dose is 20  $\mu$ g. Subjects randomised to GONAL-F will receive a daily starting dose of 225 IU which will be fixed for at least the first four stimulation days. Dose adjustments may be implemented on the day of starting the GnRH antagonist (stimulation day 5 or day 6) or later, and can occur no more frequently than once every second day. At each dose adjustment, the daily GONAL-F dose may be adjusted by 75 IU based on the subject's response. The minimum GONAL-F dose is 75 IU and the maximum GONAL-F dose is 300 IU. Subjects can be treated with rFSH for a maximum of 20 days, and coasting is not allowed.

To prevent a premature LH surge, a GnRH antagonist (ganirelix acetate, FYREMADEL, SUN Pharma) will be initiated on stimulation day 5 or day 6 at a daily dose of 0.25 mg and continued throughout the stimulation period. Triggering of final follicular maturation will be done as soon as  $\geq$ 3 follicles with a diameter  $\geq$ 17 mm are observed (i.e. on the day or the day after). Triggering can also be done in case 1 or 2 follicles with a diameter  $\geq$ 17 mm are observed and the investigator judges that  $\geq$ 3 follicles with a diameter  $\geq$ 17 mm cannot be reached, and that triggering

is preferred instead of cycle cancellation. The triggering drug will be either human chorionic gonadotropin (hCG) or GnRH agonist, depending on the extent of ovarian response and whether transfer in the fresh cycle or in a subsequent frozen cycle (including a freeze-all approach) is intended. If transfer in the fresh cycle is intended, 250 µg hCG (choriogonadotropin alfa, OVITRELLE, Merck) will be administered. If there are  $\geq$ 25 follicles with a diameter  $\geq$ 12 mm or the serum estradiol is  $\geq$ 5,000 pg/mL (18,355 pmol/L) (local laboratory) or a freeze-all approach is intended, 0.2 mg GnRH agonist (triptorelin acetate, GONAPEPTYL, Ferring) will be administered. Moreover, if these criteria for triggering with GnRH agonist are not met, but the investigator judges that the subject is at risk of developing OHSS and that triggering with hCG is not advisable, the subject can undergo triggering with GnRH agonist. In case of poor ovarian response, defined as the investigator judging that the triggering criterion cannot be reached by day 20, the cycle is to be cancelled. In case of excessive ovarian response, defined as the investigator judging that triggering of final follicular maturation is not advisable due to safety concerns, the cycle is to be cancelled. The number and size of follicles at the end-of-stimulation will be recorded.

Oocyte retrieval will take place 36h (±2h) after triggering of final follicular maturation. All oocytes from follicles with an estimated diameter  $\geq$ 12 mm must be retrieved. The oocytes can be inseminated by IVF and/or ICSI. Fertilisation will be assessed on day 1 after oocyte retrieval. The number and quality of blastocysts will be assessed at the last day of culture, i.e. day 5 or day 6 (as applicable) after oocyte retrieval. The day 5 / day 6 blastocyst quality assessment will be based on the Gardner & Schoolcraft blastocyst scoring system. Blastocysts that are not transferred in the fresh cycle will be cryopreserved in accordance with local guidelines and/or regulations.

Blood samples will be collected at stimulation day 1 for measurement of AMH, estradiol and progesterone as well as at end-of-stimulation for measurement of estradiol and progesterone. For subjects who provide additional, optional consent, blood samples will be collected at stimulation day 1 for potential future analysis of possible biomarkers associated with ovarian response.

For subjects who undergo triggering of final follicular maturation, the end-of-trial visit must take place 9-14 days after triggering to cover the assessment of early OHSS (onset  $\leq$ 9 days after triggering). For subjects who do not undergo triggering of final follicular maturation, the end-of-trial assessments must be performed at the subject's last scheduled trial visit (or alternatively at a separate end-of-trial visit within 7 days of the last scheduled trial visit). If trial procedures and/or assessments are to be performed on Sundays, public holidays or outside the opening hours of the clinic, the procedures and/or assessments can be postponed to the upcoming weekday (maximum one day after original visit schedule).

#### Follow-up Period – First Transfer Cycle

Follow-up information will be collected from the subject's first transfer cycle, irrespective of whether the first transfer takes place in a fresh or frozen cycle. This follow-up covers cycles with the transfer procedure occurring within 3 months after start of stimulation.

[figure not shown]
Depending on blastocyst availability, it is expected that subjects who underwent triggering of final follicular maturation with hCG will undergo transfer on day 5 after oocyte retrieval and that

subjects who underwent triggering of final follicular maturation with GnRH agonist will undergo transfer in a frozen cycle using blastocysts cryopreserved on day 5 or day 6 after oocyte retrieval. The number of transferred blastocyst(s) in the first fresh or frozen cycle will be based on the subject's wishes and the investigator's recommendation and in accordance with local guidelines and/or regulations. The number and quality of transferred blastocyst(s) will be recorded. Luteal phase support in fresh and frozen cycles as well as potential other medicinal products for programming of frozen cycles will be in accordance with the site's clinical practice.

Clinical pregnancy in the first transfer cycle will be assessed by transvaginal ultrasound 5-6 weeks (35-48 days) after transfer, and the number of gestational sacs will be recorded. For subjects who undergo transfer in the fresh cycle, assessment of late OHSS (onset >9 days after triggering) will take place during the follow-up period.

#### 3.1.1 Trial Design Diagrams

[figure not shown]
A diagram illustrating the trial period is shown in Figure 3-1.

OR: Oocyte retrieval; TVU: Transvaginal ultrasound

#### Figure 3-1 Trial Diagram – Trial Period

A diagram illustrating the follow-up period in the first transfer cycle is shown in Figure 3-2.

TVU: Transvaginal ultrasound

#### Figure 3-2 Trial Diagram – Follow-up Period (First Transfer Cycle)

#### 3.1.2 Trial Flow Chart – Subject Procedures

The flow of the trial procedures for subjects is shown in Table 3-1.

Table 3-1	Trial Flow Chart – Subject Procedures
-----------	--

	Screening	Stimulation		Oocyte retrieval	End	
		Start of stimulation	Start of GnRH antagonist	End-of-stimulation		End-of-trial a)
	<90 days before randomisation	Day 1	Day 5 or day 6 b)	End	36h ± 2h after triggering	
Written informed consent	Х					
Inclusion/exclusion criteria	Х	X c)				
Demographics	Х					
Medical history	Х					
Infertility history	Х					
Body weight, height	Х					
Physical examination	Х					Х
Gynaecological examination	Х					Х
Urinary pregnancy test	Х	X c)				
Transvaginal ultrasound		X c)		Х		
Blood collection, endocrine d)		X c)		Х		
Blood collection, potential biomarkers e)		X c)				
Randomisation		Х				
IMP dispensing		Х	Х			
NIMP dispensing			Х	Х		
Oocyte retrieval					Х	
Drug accountability			Х	Х	Х	
Concomitant medication	Х	Х	Х	Х	Х	Х
Adverse events	Х	Х	Х	Х	Х	Х

a) For subjects who undergo triggering of final follicular maturation, the end-of-trial visit must take place 9-14 days after triggering to cover the assessment of early OHSS (onset ≤9 days after triggering). For subjects who do not undergo triggering of final follicular maturation, the end-of-trial assessments must be performed at the subject's last scheduled trial visit (or alternatively at a separate end-of-trial visit within 7 days of the last scheduled trial visit).

b) GnRH antagonist will be initiated on stimulation day 5 or day 6.

c) Performed before the first IMP dose.

d) Stimulation day 1: AMH, estradiol and progesterone; end-of-stimulation: estradiol and progesterone.

e) Additional, optional, consent required.

GnRH: gonadotropin-releasing hormone, IMP: investigational medicinal product, NIMP: non-investigational medicinal product, OHSS: ovarian hyperstimulation syndrome

#### 3.1.3 Trial Flow Chart - Oocyte / Blastocyst Procedures

The flow of the trial procedures for oocytes and blastocysts is shown in Table 3-2.

Table 3-2         Trial Flow Chart – Oocyte / Blastocyst Procedures	
---	--

	Day 0 (OR)	Day 1 after OR	Day 5 after OR	Day 6 after OR
Oocyte retrieval (OR)	X			
Insemination by IVF and/or ICSI	X			
Assessment of oocyte fertilisation		Х		
Assessment of blastocyst quality a)			X	Х
Transfer in fresh cycle, if applicable			X	
Cryopreservation			Х	Х

a) Assessment to be performed on last day of culture only.

ICSI: intracytoplasmic sperm injection, IVF: in vitro fertilisation, OR: oocyte retrieval

#### **3.2** Determination of Sample Size

In a previous trial (MERIT), 347 subjects aged 22-37 years were treated with a starting dose of 225 IU GONAL-F. In these subjects the mean number of oocytes retrieved was 11.8 and the standard deviation was 5.7. Assuming that the standard deviation for number of oocytes retrieved in this trial will be 6.0, a total sample size of 300 with a 2:1 randomisation will give a 2-sided 95% confidence interval ranging from -1.44 to +1.44 oocytes from the observed difference. This level of precision is considered as sufficient and is also more precise than the equivalence limits of  $\pm 3$  oocytes that has been applied in previous trials comparing biosimilar FSH compounds.

## **4 SUBJECT DISPOSITION**

The subject disposition will include all screened subjects and describe the number of randomised, treated, completed and discontinued subjects, including reason for discontinuation. Screened subjects who discontinue from the trial prior to randomisation are classified as screening failures. Screening failures and the primary reason for screening failure will be described. Subject disposition with respect to analysis sets will also be tabulated and will include the number of subjects in the Intention-To-Treat (ITT) Analysis Set, the Full Analysis Set (FAS), the Per-Protocol (PP) Analysis Set and the Safety Analysis Set. Subject disposition tables will be produced overall and by AMH level at stimulation day 1 (AMH <15 pmol/L, AMH ≥15 pmol/L, or missing) and will include the two treatment groups (i.e. REKOVELLE and GONAL-F) and a total column.

# **5 PROTOCOL DEVIATIONS**

Important protocol deviations (PDs) will be rated as either minor or major. Protocol deviations substantially impacting the primary endpoint and thereby affecting the conclusions of the trial will be rated as major. Major protocol deviations will lead to exclusion of data from the PP analysis set. Data will not be excluded from the data analysis in case of minor protocol deviations.

The rating of the important PDs as 'minor' and 'major' will be decided by the Statistician and Medical responsible based on a blinded review of data before declaration of clean file and lock of database. Major protocol deviations will be summarised by category and treatment group to reflect general protocol adherence.

Major protocol deviations will be tabulated and listed by subject for the FAS. The list will be sorted by country, centre and subject number.

#### 6 ANALYSIS SETS

#### 6.1 Intention-To-Treat Analysis Set

The intention-to-treat (ITT) analysis set comprises all randomised subjects. Subjects will be analysed according to the planned (randomised) treatment.

#### 6.2 Full Analysis Set

The full analysis set (FAS) will consist of all randomised subjects exposed to IMP. Subjects will be analysed according to the planned (randomised) treatment.

#### 6.3 Per-Protocol Analysis Set

The Per-Protocol (PP) analysis set is defined as all randomised and exposed subjects except those with major protocol deviations as described in Section 5.

#### 6.4 Safety Analysis Set

The safety analysis set will consist of all randomised subjects exposed to IMP. Subjects will be analysed according to the actual treatment received.

#### 7 TRIAL POPULATION

#### 7.1 Demographics and other Baseline Characteristics

All relevant baseline data obtained before first exposure to IMP will be based on the FAS and tabulations will be produced overall and by AMH level at stimulation day 1 (AMH<15 pmol/L, AMH  $\geq$ 15 pmol/L, or missing) and will include both treatment groups and a total column. Baseline data will not be compared using statistical tests. Continuous variables will be presented with number of subjects, mean, standard deviation, median, inter-quartile range, minimum and maximum. Categorical variables will be presented with number and percentage of subjects within each specific category. Missing data will not be imputed.

# 7.1.1 Demographics

The following demographic information will be tabulated: Age at randomisation (years), age category at randomisation (<35, 35-37, 38-40), ethnicity, race and country.

## 7.1.2 Body Measurements

The following body measurements at screening will be summarised: Body weight (kg), body weight category (<45, 45-<55, 55-<65, 65-<75, 75-<85, 85-<95,  $\geq95$ ), height (m), BMI (kg/m^2), BMI category (<18.5, 18.5-<25.0, 25.0-<30.0,  $\geq30.0$ ).

#### 7.1.3 Endocrine Parameters

The following endocrine parameters measured at stimulation day 1 will be tabulated: AMH (pmol/L), AHM category (<15 pmol/L,  $\geq$ 15 pmol/L, missing), progesterone (nmol/L) and estradiol (pmol/L).

#### 7.1.4 Transvaginal ultrasound

The number of antral follicles on stimulation day 1 will be summarised and tabulated using categories (0-4, 5-9 and  $\geq$ 10 antral follicles).

## 7.1.5 Medical History

Medical history recorded at screening will be coded using the Medical Dictionary for Regulatory Activities (MedDRA) and summarised. The version of MedDRA will be documented.

## 7.1.6 Infertility History and Previous Fertility Treatment

The following data on infertility history will be tabulated: Number of subjects with primary infertility, duration of infertility (months) and primary reason for infertility.

The following data on previous fertility treatment cycles will be tabulated: Number of subjects with at least one previous fertility treatment cycle and number of previous fertility treatment cycles per subject.

## 7.1.7 Gynaecological Examination

Gynaecological examination performed at screening covers the categories breast, external genitalia, vagina, cervix, uterus, ovaries and fallopian tubes. Each category will be evaluated as normal, abnormal not clinically significant or abnormal clinically significant. Gynaecological examination at screening will be summarised by category.

## 7.1.8 Physical Examination

Physical examination performed at screening covers the categories general appearance, central and peripheral nervous system, head and neck, respiratory system, cardiovascular system, gastrointestinal system, lymphatic system, urinary system, musculoskeletal system and skin. Each category will be evaluated as normal, abnormal not clinically significant, abnormal clinically significant or not done. Physical examination at screening will be summarised by category.

# 8 PRIOR AND CONCOMITANT MEDICATION

Medications will be coded using the World Health Organization Drug Reference List and categorised as either

- Prior medication: medication taken exclusively prior to treatment (i.e. with stop date/time before date/time of first IMP administration)
- Concomitant medication: medication taken during the treatment period (i.e. medication that was not stopped before date/time of first IMP administration and not started after the end-of-trial visit)

If the timing of the dose of a concomitant medication cannot be established in relation to the administration of IMP, it will be considered as concomitant medication.

Prior and concomitant medication will be summarised by Anatomical Therapeutic Chemical Classification System (ATC) classification first level (alphabetically) and ATC classification second level for the FAS and produced by treatment group and in total.

# 9 EXPOSURE AND TREATMENT COMPLIANCE

## 9.1 Extent of Exposure

Duration of treatment (days) is defined as the number of days from first exposure to the day of last exposure (both inclusive). If a subject misses an intermediate dose she will still be considered as being under treatment. Tabulations will be produced for the Safety Analysis Set and the FAS (in case they differ) and will include both treatment groups and a total column.

## 9.1.1 IMP (Gonadotropins)

Exposure to gonadotropins will be summarised as the total dose administered, the average daily dose and duration of treatment (days). The total dose will be reported in  $\mu$ g for REKOVELLE and both in IU and  $\mu$ g for GONAL-F (using the conversion factor of 150 IU=11  $\mu$ g). This table will be produced overall and for subjects that completed stimulation, i.e. subjects that had hCG or GnRH agonist administered for triggering of final follicular maturation.

## 9.1.2 GnRH Antagonist

Exposure to GnRH antagonist will be summarised as the total dose administered (mg) and duration of treatment (days). This table will be produced overall and for subjects that completed stimulation, i.e. subjects that had hCG or GnRH agonist administered for triggering of final follicular maturation.

## 9.1.3 Triggering of Final Follicular Maturation

Triggering of final follicular maturation will be done by either an injection of hCG or GnRH agonist. The drug used for triggering (hCG or GnRH agonist) will be tabulated for subjects undergoing triggering.

## 9.1.4 Treatment Compliance

Subjects not receiving the scheduled dose will be listed by centre and subject number.

#### 10 EFFICACY

Unless otherwise specified, analyses of efficacy endpoints will be based on the FAS and summary tables for the primary and secondary efficacy endpoints will be presented in total and by treatment group. Continuous variables will be presented with number of subjects, mean, standard deviation, median, inter-quartile range, minimum, and maximum. Categorical variables will be presented with number and percentage of subjects within each specific category.

Results of statistical analyses will be based on least-squares means using the observed margins and include the estimated treatment difference (or ratio), a 95% confidence interval for the difference (or ratio), and the p-value for the test of no treatment difference. All analyses are of descriptive nature and no adjustments for multiple tests will be applied.

Missing observations for the endpoints number of oocytes retrieved, number of fertilised oocytes, and number of blastocysts will be replaced with zero (i.e. worst-case imputation technique) irrespective of the reason why data is not recorded. For pregnancy data, lack of data will be interpreted as a negative pregnancy.

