# 9.7.2 Primary Endpoint

The primary endpoint, number of oocytes retrieved, will be compared between REKOVELLE and GONAL-F using a negative binomial model with treatment and AMH level at stimulation day 1 (AMH <15 pmol/L, AMH  $\geq$ 15 pmol/L, or missing) as factors. The absolute treatment difference in number of oocytes retrieved, the associated 95% confidence interval, and the p-value for no treatment difference will be derived from the model estimates using the delta method.

The distribution of the number of oocytes retrieved will be described using kernel estimates. Furthermore, the ovarian response will be grouped according to the following classification:

- <4 oocytes or cycle cancellation due to poor ovarian response
- 4-7 oocytes
- 8-14 oocytes
- 15-19 oocytes
- $\geq 20$  oocytes or cycle cancellation due to excessive ovarian response
- Cycle cancellation due to another reason than poor or excessive ovarian response

The treatment difference will also be investigated for the two sub-groups AMH <15 pmol/L and AMH  $\geq$ 15 pmol/L using the same methods as above.

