#### **10.1 Primary Efficacy Endpoint**

The primary endpoint, number of oocytes retrieved, will be compared between REKOVELLE and GONAL-F using a negative binomial regression model with treatment and AMH level at stimulation day 1 (AMH <15 pmol/L, AMH  $\geq$ 15 pmol/L, or missing) as factors. The absolute treatment difference in number of oocytes retrieved, the associated 95% confidence interval, and the p-value for no treatment difference will be derived from the model estimates using the delta method.

The distribution of the number of oocytes retrieved will be visualised in histograms. Furthermore, the number of oocytes will be grouped and presented in tables and figures using the following classification:

- <4 oocytes or cycle cancellation due to poor ovarian response
- 4-7 oocytes
- 8-14 oocytes
- 15-19 oocytes
- $\geq 20$  oocytes or cycle cancellation due to excessive ovarian response
- Cycle cancellation due to another reason than poor or excessive ovarian response

The treatment difference will also be investigated for sub-groups defined by AMH level at stimulation day 1 (i.e. <15 pmol/L, AMH  $\geq$ 15 pmol/L or missing) using the same methods as above for each sub-group separately.

No formal hypothesis testing will be conducted using these methods.

As a supplementary analysis, the analysis of the primary endpoint will be repeated using the PP analysis set and corresponding summary tables will be presented.

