#### Number of Follicles at End-of-stimulation

The follicle cohort at end-of-stimulation (EOS) will be summarised by treatment on the subject level (i.e. total number of follicles, and number of follicles  $\geq 10 \text{ mm}$ ,  $\geq 12 \text{ mm}$ ,  $\geq 15 \text{ mm}$  and  $\geq 17 \text{ mm}$ ). Additionally, the mean number of follicles  $\geq 10 \text{ mm}$ ,  $\geq 12 \text{ mm}$ ,  $\geq 15 \text{ mm}$  and  $\geq 17 \text{ mm}$  at EOS will (in separate analyses) be compared between treatments using the same negative binomial regression model as used for the primary endpoint.

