# Serum Concentrations of Estradiol and Progesterone at End-of-stimulation

Serum concentrations of estradiol and progesterone at EOS will be compared between treatments using analysis of covariance (ANCOVA) models with treatment and AMH level at stimulation day 1 (AMH <15 pmol/L, AMH  $\geq$ 15 pmol/L, or missing) as factors and with the serum concentration (log-transformed) at stimulation day 1 as a covariate. Multiplicative models will be used, i.e. the serum concentrations will be log-transformed before analysis. The results of the analyses will be back-transformed and presented as estimated geometric means and mean treatment ratios with 95% confidence intervals and p-values. Values below the lower limit of quantification (LLOQ) will be estimated with LLOQ/2. Potential values above the upper limit of quantification (ULOQ) will be included as ULOQ.

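### SAP Section 10 scores any unrecorded oocyte, fertilised-oocyte or blastocyst count as zero, which is wider than the protocol's rule and gives a false zero when a retrieval took place

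*Combined protocol and SAP*

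**What the plan says.** **SAP Section 10 (Efficacy)** covers three endpoints: oocytes retrieved, fertilised oocytes and blastocysts. A missing observation for any of them is "replaced with zero (i.e. worst-case imputation technique) irrespective of the reason why data is not recorded".

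**Protocol 9.7.1 (General Considerations)** says that missing data are in general not imputed. Its exception is that subjects without oocyte retrieval count as zero for the same three endpoints.

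**SAP Section 1** lets the SAP prevail over the protocol and says that the main changes are described in Section 13. Section 13 lists the per-protocol analysis, the new models for fertilisation and implantation rates, and the analysis set for exposure. The wider zero rule is not there.

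**SAP 10.1** analyses the primary endpoint on the FAS and within AMH subgroups. As a supplement, "the analysis of the primary endpoint will be repeated using the PP analysis set". It adds: "No formal hypothesis testing will be conducted using these methods".

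**The concern.** The SAP rule treats two situations alike. If a cycle is cancelled before retrieval, no oocytes were retrieved and zero is a fact. If a retrieval took place and the count was not recorded, the count is unknown and very probably not zero. The protocol's wording keeps these apart and the SAP's does not.

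The worst-case label adds to the problem. Zero is the lowest value one subject can have, but the trial estimates a difference between arms, and protocol 3.5.4 expects a similar number of oocytes in the two. For that purpose zero has no fixed direction. In the REKOVELLE arm it counts against REKOVELLE, and in the GONAL-F arm it counts in its favour. Equal shares in both arms pull any true difference towards nil.

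Since the analyses are descriptive, readers will judge similarity from the primary estimate and its interval. The values behind that estimate should be observed or openly missing.

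**Working it through.** **1. The plan's own figure.** Inputs from SAP 3.2 and the protocol synopsis: SD 6.0, 200 and 100 subjects, two-sided 95% interval.

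Half-width = 1.96 × 6.0 × √(1/200 + 1/100) = 1.44. This reproduces the stated value.

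**2. One unknown count scored zero.** Assume it would have averaged 11.8, the mean in the previous trial cited in SAP 3.2.

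- REKOVELLE arm: 11.8/200 = 0.059 oocytes, or 0.059/1.44 = 4% of the half-width.
- GONAL-F arm: 11.8/100 = 0.118 oocytes, or 0.118/1.44 = 8% of the half-width.

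**3. Shares of unknown counts.** With shares mR and mG scored zero, the shift in REKOVELLE minus GONAL-F is −11.8 × (mR − mG). The documents give no rates, so these are assumptions.

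| Assumed shares (REKOVELLE v GONAL-F) | Effect on the difference |
|---|---|
| 5% v 0% | −0.59 |
| 0% v 5% | +0.59 |
| 5% v 5%, true difference 0 | 0.00 |
| 5% v 5%, true difference 3 | 3 × 0.95 = 2.85 |

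A shift as large as the half-width needs an imbalance of 1.44/11.8 = 12.2 percentage points. A simulation of the negative binomial model (treatment factor only, 300 trials per setting) agreed: mean differences of −0.56 and +0.55 in the first two rows, and about 0 in the third.

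**4. Does any planned analysis vary the rule?** The FAS analysis, the AMH subgroups and the per-protocol repeat all apply it. The per-protocol set (SAP 6.3) removes major protocol deviations, and an unrecorded count is not defined as one. If the blinded review rated one as major, that subject would leave along with others removed for unrelated reasons.

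**5. How could a count be unknown?** Protocol 7.1.1 has the count recorded at the retrieval visit and protocol 10.1 requires it in the source documents, so an unrecorded count after a retrieval should be rare. Under protocol 4.3.3, no further data are obtained once consent is withdrawn. That could leave retrieval status unknown, or fertilisation and blastocyst counts unknown after a recorded retrieval.

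**The case against.** **The stronger reading.** A reader might infer that zero is wrong for cycles cancelled for excessive response: some of the strongest responders get the lowest value, while the response table puts them in the class of 20 or more "oocytes or cycle cancellation due to excessive ovarian response". The documents do not support calling this a bias or a contradiction.

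- The endpoint is oocytes retrieved. Protocol 6.2.3 sends cancelled cycles to the end-of-trial assessments, so zero is the literal count, and protocol 9.7.1 fixed it in advance.
- The table is openly composite. Protocol 9.7.2 says that "the ovarian response will be grouped according to the following classification", which is a different quantity.
- These women are visible elsewhere: in the preventive-intervention summary and, through reasons for discontinuation, in the disposition tables. Other views of response do not use the zero rule. "The number and size of follicles at the end-of-stimulation will be recorded", and follicle counts by size threshold will "be compared between treatments using the same negative binomial regression model as used for the primary endpoint". Likewise, "Serum concentrations of estradiol and progesterone at EOS will be compared between treatments using analysis of covariance (ANCOVA) models".
- Such cancellations are probably rare. An agonist trigger is available, doses can be adjusted, and women with polycystic ovarian syndrome, previous OHSS or exuberant response are excluded. Assessors are blinded, so with equal true response the expected shift is nil.

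Setting these subjects to 20 instead of zero changes the difference by about 0.18 oocytes per percentage point of imbalance in the fitted model. That comes from simulated negative binomial counts with GONAL-F mean 11.8, SD 6.0 and two equal AMH classes with assumed means 9.3 and 14.3; cancelled subjects were drawn from counts of 20 or more. Four REKOVELLE cancellations against none (2 points) give −0.36. With the same assumed cancellation probability in both arms (0.5%, 1% or 2%), chance produces a shift of 0.40 or more in either direction about 1%, 6% or 18% of the time. This measures a change of question, not an error.

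**Against the remaining point.** The SAP is entitled to prevail and promises only main changes in Section 13. Deleting a label changes no result, and few counts are likely to be affected. All of that stands and sets the severity. It does not make zero a correct value for a retrieval whose count was not recorded.

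**Conclusion.** The point holds as a small rule correction. The SAP widens the protocol's zero rule without listing the change, and as written it gives a false zero to any retrieval with an unrecorded count. No analysis of the primary endpoint varies this. The worst-case description does not fit a difference between arms.

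The size is about 0.06 (REKOVELLE) or 0.12 (GONAL-F) oocytes per affected subject. This rests on an assumed mean of 11.8 for the unknown counts and on arms of 200 and 100. The number affected is unknown and should be small. The sample-size figure is untouched, and no bias in the primary result is claimed. Severity: minor, an improvement the sponsor could make.

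**What to change.** 1. In SAP Section 10, restrict zero to subjects with no oocyte retrieval, as in protocol 9.7.1. Treat a count unrecorded after a retrieval as missing for all three endpoints, and report such cases by arm. State how a subject with unknown retrieval status is handled. If the wider rule is kept, list it in Section 13 with a reason.
2. Remove the worst-case label in the same edit.
3. Optional: pre-specify one sensitivity run of the primary model with excessive-response cancellations set to 20, the lower bound of the SAP's top class. Label it as addressing ovarian response and not oocytes retrieved, show cancellation counts by arm and reason, and list it in Section 13 beside the per-protocol analysis. It tests only this one kind of zero.

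The cost is SAP wording and at most one extra table. Treating a count as missing drops that subject from the model, which is acceptable if cases are few and reported. The value 20 is a convention, since excessive response is an investigator's safety judgement, so it belongs only in a sensitivity analysis.
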